**Table 8.1.4.2-1: 95% CI for Rate Differences When Observed in 75 Subjects per Arm and 150 Subjects per Dosing Regimen**

75 Subjects per Arm		
Coadministration Arm	Fixed Dose Combination Arm	Rate Difference (95% CI)
14%	14%	0% (-11.1%, 11.1%)
14%	12%	2% (-8.8%, 12.8%)
16%	14%	2% (-9.4%, 13.4%)
18%	16%	2% (-10%, 14%)
20%	18%	2% (-10.6%, 14.6%)
150 Subjects Each in Part D1-Q4W and Part D1-Q2W		
Q2W	Q4W	Rate Difference (95% CI)
14%	14%	0% (-7.9%, 7.9%)
14%	12%	2% (-5.6%, 9.6%)
16%	14%	2% (-6.1%, 10.1%)
18%	16%	2% (-6.5%, 10.5%)
20%	18%	2% (-6.9%, 10.9%)

Also, with 75 subjects per arm, there is a 99% probability that the 95% CI for the geometric mean ratio of Cmax of FDC to coadministration is wholly contained within [0.8, 1.25]. log(Cmax) is assumed to follow a normal distribution and, with intrasubject coefficients of variation, is assumed to be no greater than 30%.

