**Table 7: 95% CI for Rate Differences When Observed in 75 Subjects per Arm and 150 Subjects per Dosing Regimen**

75 Subjects per Arm		
Coadministration Arm	Fixed Dose Combination Arm	Rate Difference (95% CI)
14%	14%	0% (-11.1%, 11.1%)
14%	12%	2% (-8.8%, 12.8%)
16%	14%	2% (-9.4%, 13.4%)
18%	16%	2% (-10%, 14%)
20%	18%	2% (-10.6%, 14.6%)

150 Subjects Each in Part D1-Q4W and Part D1-Q2W		
Q2W	Q4W	Rate Difference (95% CI)
14%	14%	0% (-7.9%, 7.9%)
14%	12%	2% (-5.6%, 9.6%)
16%	14%	2% (-6.1%, 10.1%)
18%	16%	2% (-6.5%, 10.5%)
20%	18%	2% (-6.9%, 10.9%)

Also, with 75 subjects per arm, there is a 99% probability that the 95% CI for the geometric mean ratio of Cmax of FDC to coadministration is wholly contained within [0.8, 1.25]. log(Cmax) is assumed to follow a normal distribution and, with intrasubject coefficients of variation, is assumed to be no greater than 30%.

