### **3.1.2.5 *Part D Melanoma Prior IO Extended Expansion (Coadministration or Treatment with Fixed-dose Combination [BMS-986213])***

In Part D, advanced melanoma subjects with progression on prior anti-PD-1 therapy will be enrolled into 2 subparts, D1 and D2, based on eligibility criteria. If eligible for the focused (more restricted eligibility) D1 subpart, subjects will be randomized across 3 arms:

Arm 1: BMS-986016 80 mg + nivolumab 240 mg given by coadministration Q2W

Arm 2: BMS-986016 160 mg + nivolumab 480 mg given by coadministration Q4W

Arm 3: BMS-986213 (relatlimab 160 mg/nivolumab 480 mg) given Q4W; BMS-986213 contains both relatlimab and nivolumab in the same solution at a ratio of 1:3 (relatlimab:nivolumab)

Randomization will be unblinded. Enrollment and randomization to Arm 1 may continue until the following criteria are met: (a) 90 efficacy-evaluable LAG-3-positive subjects have been treated, (b) 60 efficacy-evaluable LAG-3-positive and BRAF WT subjects have been treated, and (c) 60 efficacy-evaluable LAG3-positive and ipilimumab-pretreated subjects have been treated.

Enrollment and randomization across Arms 2 and 3 may continue until the following criteria are met: (a) 90 efficacy-evaluable LAG-3-positive subjects have been treated, (b) 60 efficacy-

evaluable LAG-3-positive and BRAF WT subjects have been treated, and (c) 60 efficacy-evaluable LAG-3-positive and ipilimumab-pretreated subjects have been treated.

Prior to Revised Protocol 09, Part D1 subjects are being enrolled only into Arm 1. Subsequent to activation of this revised protocol and until the enrollment to Arm 1 is completed, subjects in Part D1 will be randomized 1:1:1 across the 3 arms. Once enrollment to Arm 1 is completed, subjects will be randomized 1:1 to Arms 2 and 3. If enrollment to Arms 2 and 3 is completed prior to Arm 1, then enrollment to Arm 1 will be completed as a single arm. Prior to the start of randomization, a safety lead-in will be conducted with BMS-986213.

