**8.1.4.2 Melanoma Prior IO Focused Eligibility Expansion (Part D1-Q4W)**

The coprimary objective in Part D1-Q4W is to evaluate the difference in safety between coadministration relative to FDC as measured by the incidence of AEs in the Broad Scope MedDRA Anaphylactic Reaction SMQ occurring within 2 days after dosing during the combination and to confirm with Q4W dosing of BMS-986016 160 mg in combination with nivolumab 480 mg the safety of the BMS-986016 80 mg in combination with nivolumab 240 mg Q2W in advanced melanoma subjects who progressed while on anti-PD-1 antibody therapies (see [Appendix 5](#)).

Prior to Revised Protocol 09, subjects are being enrolled into a single arm: Part D1 BMS-986016 80 mg + nivolumab 240 mg Q2W. Subsequent to this amendment, and until the enrollment to Part D1 BMS-986016 80 mg + nivolumab 240 mg Q2W is completed, subjects in Part D1 will be randomized 1:1:1 to Part D1 BMS-986016 80 mg + nivolumab 240 mg Q2W, Part D1 BMS-986016 160 mg + nivolumab 480 mg Q4W coadministration, and Part D1 BMS-986213 (relatlimab 160 mg/nivolumab 480 mg) Q4W arms. Once enrollment to Part D1 BMS-986016 80 mg + nivolumab 240 mg Q2W is completed, subjects will be randomized 1:1 to Part D1 BMS-986016 160 mg + nivolumab 480 mg Q4W coadministration and Part D1 BMS-986213 (relatlimab 160 mg/nivolumab 480 mg) Q4W arms. If enrollment to Q4W arms is completed prior to arm BMS-986016 80 mg + nivolumab 240 mg Q2W, then enrollment to arm BMS-986016 80 mg + nivolumab 240 mg Q2W will be completed as a single arm.

Approximately 150 subjects will be randomized to the 2 treatment arms Part D1 BMS-986016 160 mg + nivolumab 480 mg Q4W coadministration and Part D1 BMS-986213 (relatlimab 160 mg/nivolumab 480 mg) Q4W. This number of treated subjects was chosen to achieve a sufficient level of precision for a descriptive analysis to estimate the difference in rates of AEs in the Broad Scope MedDRA Anaphylactic Reaction SMQ between the 2 treatment arms. Seventy-five (75) treated subjects per arm will allow estimation of the rate difference within 95% confidence limits of  $\pm 15\%$  or less and will be supplemented by a qualitative clinical assessment of the type and severity of events to evaluate benefit-risk (see [Appendix 5](#)).

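### The 99% Cmax-ratio probability for FDC versus coadministration cites an intrasubject CV, but the arms are parallel, so it holds only if the 30% is the total CV and the true ratio is 1.00

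*Combined protocol and SAP*

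**What the plan says.** The paragraph after Table 8.1.4.2-1 in Section 8.1.4.2 says that "with 75 subjects per arm, there is a 99% probability that the 95% CI for the geometric mean ratio of Cmax" of FDC to coadministration falls entirely between 0.8 and 1.25. The variability input is that "log(Cmax) is assumed to follow a normal distribution and, with intrasubject coefficients of variation, is assumed to be no greater than 30" percent. The Synopsis repeats both statements below its Table 7. Neither place gives a total or between-subject CV for Cmax, a source for the 30%, or the true ratio assumed.

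Section 3.1.2.5 describes the allocation. Arm 2 is coadministration and Arm 3 is FDC, both Q4W. Part D1 subjects are randomized across three arms and, once Arm 1 is full, "subjects will be randomized 1:1 to Arms 2 and 3". No crossover between the two products is described.

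On the number of subjects, Section 8.1.4.2 states: "Approximately 150 subjects will be randomized to the 2 treatment arms". The reason given there is the precision of the difference in Broad Scope Anaphylactic Reaction SMQ rates. Section 1.3.2 lists the FDC versus coadministration PK comparison as a secondary objective. Section 8.4.4 reports it descriptively, with point estimates and CIs for the geometric mean ratios of Cmax and AUC(TAU).

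**The concern.** An intrasubject CV describes how Cmax varies within one person from occasion to occasion. It is the right input when each subject receives both products and serves as their own control. Here the ratio compares the means of two different groups of people, so differences between people do not cancel. The standard error depends on the total variance of log(Cmax).

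The protocol gives reason to think the between-subject part is not zero. Section 1.1.9.1 describes flat dosing studied in adults weighing 40 to 120 kg. Section 1.4.1.4.1 reports that body weight affects relatlimab central volume, and that weight, sex, albumin and LDH affect its clearance.

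At stake is the only precision statement the plan makes for this PK comparison. If it is too optimistic, a reported CI that crosses 0.8 or 1.25 could be taken as a sign of a product difference when the cause is variance understated at planning.

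**Working it through.** **Inputs from the documents.** 75 subjects per arm, two independent groups; two-sided 95% CI; limits 0.8 and 1.25, that is ±ln(1.25) = ±0.2231 on the log scale; CV 30%.

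**Input not in the documents.** True ratio, taken as 1.00.

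**Formulas.** SD of log(Cmax): s = √ln(1 + CV²). Standard error of the log ratio: SE = s·√(2/75). The CI lies inside the limits when the estimated log ratio is within ±(0.2231 − t·SE), with SE estimated on 148 degrees of freedom. In the normal approximation with true ratio 1.00, the probability is 2Φ(0.2231/SE − 1.96) − 1. The exact version integrates over the distribution of the estimated variance.

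**Step 1: reproduce the plan's figure, reading 30% as the total CV.**
- s = √ln(1.09) = 0.2936
- SE = 0.2936 × √(2/75) = 0.0479
- Normal approximation: 0.2231/0.0479 − 1.96 ≈ 2.69, giving 99.3%
- Exact: 99.2%; simulation: 99.4%

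The stated 99% is therefore what the parallel design yields on this reading.

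**Step 2: read 30% as intrasubject, as written, and add between-subject variance on the log scale.** Total variance = ln(1.09) + ln(1 + CV_b²). The between-subject values CV_b are assumptions.

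| Assumed between-subject CV | Total CV | Probability (exact) |
|---|---|---|
| 10% | 31.8% | 98.4% |
| 20% | 36.6% | 93.9% |
| 30% | 43.4% | 81.0% |
| 40% | 51.4% | 60.1% |

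The 30% row as an example: variance 0.0862 + 0.0862 = 0.1724, s = 0.415, SE = 0.0678. The normal approximation gives 2Φ(0.2231/0.0678 − 1.96) − 1 = 81.7%; the exact value is 81.0%.

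**Step 3: by total CV, true ratio 1.00.** 30%: 99.2%; 35%: 95.8%; 40%: 88.2%; 50%: 63.9%. The probability falls more than two points below 99% once the total CV exceeds about 34%.

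**Step 4: dependence on the true ratio.** At total CV 30%, a true ratio of 0.95 gives 94.5%.

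**Step 5: does the match in Step 1 settle which CV was meant?** No. A two-period crossover with 75 subjects in total and a within-subject CV of 30% also gives about 99%. The number is consistent with a mislabelled total CV in a parallel calculation, and with a crossover input carried into a parallel design.

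**The case against.** The strongest reply is that nothing is shown to be miscalculated. The ordinary two-group formula with 75 per arm and a 30% CV returns 99.2%, and the sentence itself says per arm, which fits a parallel calculation better than a crossover. The sentence is awkwardly built, so a wrong label is a natural explanation. The 30% is also put as an upper bound, so if it bounds the total CV, 99% is the least favourable case at a ratio of 1.00. That ratio is an ordinary planning value, and it agrees with Section 1.1.9.6, which expects the same exposure from coadministration and FDC as from sequential dosing. The larger drops in Step 2 rest on between-subject CVs that no document supplies.

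Most of this stands. A reader might infer that the 99% is wrong; the documents do not support that, because they do not say what the total CV is. A reader might also infer that 75 per arm was justified by this calculation, or that a PK bridge to the FDC depends on it. Section 8.1.4.2 contradicts the first by tying the number to adverse-event rate precision and adding the Cmax statement afterwards. Section 8.4.4 gives no support to the second, since it sets no equivalence test or pass/fail rule.

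What the reply does not remove is that the assumption as written names the wrong variance component. The reader has no total CV, source or ratio from which to confirm the 99%.

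**Conclusion.** The point holds as a fault in a stated assumption. With parallel arms, the 99% does not follow from an intrasubject CV of at most 30%. It follows (99.2%) if 30% is the total CV of Cmax and the true ratio is 1.00. If 30% is truly intrasubject, the probability is lower, from about 98% to 60% over assumed between-subject CVs of 10 to 40%. The documents do not allow a choice within that range. These figures assume normal log(Cmax), equal variances, 75 evaluable subjects per arm and a true ratio of 1.00.

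The practical weight is modest. Neither the sample size nor any PK decision rule depends on the figure; it is the stated precision of a descriptive secondary comparison. Appendix 7 records that enrollment closed on 30-Jul-2021, so the correction affects how the comparison is documented and read, not the design.

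**What to change.** In Section 8.1.4.2 and in the Synopsis text under Table 7:

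- The sponsor identifies which CV the 30% is and gives its source. This comes first, because relabelling the 30% as total without a source would assert something the documents do not establish.
- Replace the intrasubject term with the total CV of Cmax, using observed Cmax variability from earlier parts. Tables 5.5.1-1 to 5.5.1-3 schedule end-of-infusion samples in Parts B and C. Dosing there was sequential, which should be noted.
- State that the true ratio is assumed to be 1.00.
- Restate the probability for that CV and show a range: total CV 30%: 99%; 35%: 96%; 40%: 88%; 50%: 64%.

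The cost is a sentence or two in each place, plus a summary of existing PK data. The stated probability may become less favourable.

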### **8.1.4.3 Melanoma Prior IO Expanded Eligibility Expansion (Part D2)**

Part D2 will have an expanded eligibility criteria with 2 cohorts in sequence: 160 mg BMS-986016 with 480 mg nivolumab Q4W and 240 mg BMS-986016 with 480 mg nivolumab Q4W. Subjects in Part D2 on average will have a worse performance status and be more heavily treated. Approximately 30 subjects will be initially treated with 160 mg BMS-986016 with 480 mg

nivolumab Q4W. Once this dose level is deemed safe, approximately up to 220 additional subjects will be treated with either 160 mg BMS-986016 with 480 mg or 240 mg BMS-986016 with 480 mg nivolumab Q4W to establish safety and efficacy in this broader group of melanoma patients. With 30 subjects, there is approximately 96% chance to observe at least 1 occurrence of any AE that would occur with a 10% incidence in the population from which the sample is drawn. With 250 subjects, there is approximately 92% chance to observe at least 1 occurrence of any AE that would occur with a 1% incidence in the population from which the sample is drawn. Safety and efficacy data will be collected as in the other cohorts, and the data will be used as supportive evidence of safety and efficacy of the combination therapy.

### **8.1.5      *Exposure/Response Expansion Q4W Dosing (Part E)***

In Part E, 2 disease cohorts will be investigated: melanoma participants who experienced disease progression on prior anti-PD-1 therapy in the advanced, unresectable, or metastatic setting and melanoma participants who have not received prior systemic anticancer therapy for unresectable or metastatic melanoma. The objective of this expansion is to support further clinical testing at higher dose of relatlimab in combination with nivolumab by demonstrating adequate safety and tolerability as well as favorable benefit-risk by assessing preliminary efficacy measured by ORR and other clinically relevant efficacy measures such as DOR and DCR. However, the sample size is based on efficacy, specifically on the target ORR relative to the ORR observed at the lower dose of relatlimab in combination with nivolumab. Both disease cohorts will be handled independently, and there will be no multiplicity adjustment. The sample size of the melanoma cohort of participants who experienced disease progression on prior anti-PD-1 therapy is based on the comparison of the ORR of subjects who receive 480 mg BMS-986016 + 480 mg nivolumab Q4W vs the benchmark (ie, historical control) observed ORR of subjects who received 80 mg BMS-986016 + 240 mg nivolumab Q2W in this study. A sample size of 75 subjects who experienced disease progression on prior anti-PD-1 therapy will provide approximately 85% power for testing the ORR difference with a 2-sided alpha of 0.1, assuming ORR of 25% and 10% in the 480 mg BMS-986016 + 480 mg nivolumab Q4W arm and in the historical control arm, respectively.

The sample size of the cohort of participants who have not received prior systemic anticancer therapy for advanced, unresectable, or metastatic melanoma is based on the comparison of the ORR of subjects who receive 480 mg BMS-986016 + 480 mg nivolumab Q4W vs the ORR of subjects who receive 160 mg BMS-986016 + 480 mg nivolumab Q4W. A sample size of 150 subjects who have not received prior systemic anticancer therapy for unresectable or metastatic melanoma randomized in a 1:1 ratio in 2 arms will provide approximately 81% power for testing the ORR difference with a 2-sided alpha of 0.1, assuming ORR of 67% and 47% in the 480 mg BMS-986016 + 480 mg nivolumab Q4W arm and in the 160 mg BMS-986016 + 480 mg nivolumab Q4W arm, respectively.

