### **1.1.6      *Rationale for Part D Expansion***

As of the cutoff date of 15-Jun-2017, preliminary proof-of-concept efficacy has been revealed in the Part C combination treatment expansion cohort of advanced melanoma with prior treatment with anti-PD-1/PD-L1. All subjects were treated with BMS-986016 80 mg + nivolumab 240 mg every 2 weeks (Q2W). The overall ORR was 11.5% (7/61 response evaluable), with a disease control rate (DCR) of 49%. Biomarker analyses suggested that subjects whose TIL expressed more LAG-3 had a higher response rate, with a greater than 3-fold increase in ORR observed in subjects with evidence of LAG-3 expression in at least 1% of nucleated cells within the tumor margin,

compared with less than 1% LAG-3 expression (18.2% [6/33] and 5.0% [1/20], respectively). PD-L1 expression did not appear to enrich for response. The treatment group had the following characteristics: 1) most subjects had M1C disease (68%), 2) the cohort was heavily pretreated (77% with 2 or more prior therapies and 57% with prior anti-CTLA-4 therapy), 3) all subjects had progressed while receiving anti-PD-1/PD-L1, and 4) progressive disease (PD) was the best response to prior anti-PD-1/PD-L1 in 46% of subjects. Overall, anti-LAG-3 (BMS-986016) in combination with nivolumab demonstrated encouraging initial efficacy with a safety profile similar to nivolumab monotherapy.

Based on initial efficacy signal in advanced melanoma subjects who progressed on anti-PD-1/PD-L1 therapy, additional subjects in this subset population for further clinical testing are justified. Assessment in this population will be extended in 2 subparts: Part D1 and D2. D1 will test the combination in a focused eligibility population, whereas D2 will allow assessment in a broader population under expanded eligibility criteria.

Given the improved response rate in subjects whose tumor-associated immune cells express more LAG-3, efficacy analysis in Part D1 will be the primary focus. Subjects whose tumors are LAG-3 negative will also be evaluated to determine the role of LAG-3 expression on the antitumor activity of BMS-986016. Part D2 will explore safety and efficacy in a broader patient population, including those with Eastern Cooperative Oncology Group performance status (ECOG PS) up to 2 and among those with a more diverse set of prior therapies.

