In participants who experienced disease progression on prior anti-PD-1 therapy, only the BMS-986016 480 mg + nivolumab 480 mg Q4W dosing regimen will be evaluated. In the cohort of participants who have not received prior systemic anticancer therapy for unresectable or metastatic melanoma, both the BMS-986016 160 mg + nivolumab 480 mg Q4W and the BMS-986016 480 mg + nivolumab 480 mg Q4W dosing regimens will be evaluated.

The rationale for limiting the cohort of participants who experienced disease progression on anti-PD-1 therapy cohort to only the BMS-986016 480 mg + nivolumab 480 mg Q4W dosing regimen is that there is substantial clinical experience in melanoma participants who experienced disease progression on anti-PD-1 therapy with the BMS-986016 160 mg + nivolumab 480 mg Q4W dosing regimen. That substantial clinical experience will be used as a historical control for the purpose of elucidating the dose-response curve in this cohort of melanoma subjects. For the cohort of participants who have not received prior systemic anticancer therapy for unresectable or metastatic melanoma, where the clinical experience is more limited, participants will be randomized to 1 of the 2 dosing regimens.

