#### **8.1.4.1 Melanoma Prior IO Extended Expansion (Part D1-Q2W)**

Data from Part C melanoma subjects who progressed while receiving anti-PD-1 antibody therapies demonstrated a preliminary evidence that subjects with LAG-3 expression are more likely to respond to treatment of BMS-986016 in combination with nivolumab. The marker prevalence using the initial 1% cut (ie, LAG-3 expression  $\geq 1\%$ ) is estimated to be approximately 60% in this patient population.

In order to establish safety and tolerability of a more convenient dosing regimen and further characterize an enriched responder population, approximately a total of 150 subjects who meet the eligibility criteria for Part D1 will be treated with BMS-986016 80 mg + nivolumab 240 mg Q2W coadministered. A sample size of 150 is expected to provide approximately 90 subjects with LAG-3 expression using the initial cutoff of 1% and provide reasonable precision to examine the enrichment of patient population with LAG-3 expression.

Since the optimal marker cutpoint is not well known prior to the study, several different cutoffs may be explored, and, depending on the prevalence of the marker-positive using these cutoffs, the

initial total sample size may be modified in order to have an adequate precision for demonstrating preliminary clinical evidence of the treatment effect in the marker-positive population (ie, approximately 90 subjects). Although evaluation of the cutpoint will be based on the ORR, the decision of the cutpoint will be based on the totality of the efficacy data, including DOR and DCR.

Additionally, in an effort to explore an enriched patient population in advanced melanoma subjects who progressed while on anti-PD-1 antibody therapies in Part D1, other potential predictive markers such as BRAF mutation status may be explored. Approximately 60 subjects among the 90 subjects with LAG-3 expression in Part D1 are expected to be BRAF wild-type.

For the purpose of demonstrating preliminary clinical evidence of the treatment effect, the primary efficacy population will be subjects with LAG-3 expression who progressed while on anti-PD-1 antibody therapies and receive BMS-986016 80 mg + nivolumab 240 mg Q2W in Part D1. A portion of subjects in Part C who meet the eligibility criteria of Part D1 will be included in a sensitivity analysis to further strengthen the evidence.

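### The non-randomised Part E comparison (prior anti-PD-1 cohort) specifies no control for case mix, although the protocol itself reports a large, imprecise ORR difference by LAG-3 status

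*Combined protocol and SAP*

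**What the plan says.** The primary objective of Part E (Section 1.3.1) is comparative: to show a significantly higher ORR at 480 mg/480 mg Q4W, against a randomised lower dose in untreated participants and against a historical control in those who progressed on anti-PD-1 therapy.

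For the second group, Section 8.1.5 makes the comparison "vs the benchmark (ie, historical control) observed ORR of subjects who received 80 mg BMS-986016 + 240 mg nivolumab Q2W in this study". The planned 75 participants are said to give about 85% power at two-sided alpha 0.1 for 25% v 10%. The number of controls is not given. Section 1.1.7 names a different control, the experience at 160 mg/480 mg Q4W, and states: "That substantial clinical experience will be used as a historical control for the purpose of elucidating the dose-response curve in this cohort of melanoma subjects".

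The only adjustment sentence in Section 8.1.5 concerns multiplicity. Section 8.4.2 gives Clopper-Pearson and Kaplan-Meier methods; it does not mention Part E, a between-group test, a covariate, stratification or weighting. Section 4.2 states no stratification factor for the first-line randomisation.

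On LAG-3, Section 1.1.6 reports ORRs in Part C prior-anti-PD-1 melanoma at 80 mg/240 mg Q2W of "18.2% [6/33] and 5.0% [1/20], respectively" for expression of at least 1% and below 1%.

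**The concern.** An observed historical ORR reflects the patients who produced it as well as the dose. If the Part E cohort holds a larger share of LAG-3-positive patients than the control set, part of the difference in mix will be read as a benefit of the higher relatlimab dose. A smaller share would hide a real benefit. At stake is the claim that 480 mg is better than the lower dose in the prior-anti-PD-1 setting, which rests on this comparison alone because that cohort has no concurrent arm.

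The control set is also undefined in a way that bears on mix. Read literally, the wording in Section 8.1.5 takes in Part C subjects as well as Part D1 Arm 1, and under Section 3.3.1 Part C admits prior anti-PD-L1 therapy, which Part E does not.

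**Working it through.** **1. The plan's own power figure.** Inputs from Section 8.1.5: 75 Part E subjects, 25% v 10%, two-sided alpha 0.1. The number of controls is an assumption: 150, from the planned Part D1-Q2W size in Section 8.1.4.1 ("approximately a total of 150 subjects who meet the eligibility criteria for Part D1").

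Power = Φ(0.15 / √(0.25×0.75/75 + 0.10×0.90/150) − 1.645) = Φ(0.15/0.0557 − 1.645) = 85.3%, which matches the stated 85%. With 75 or 61 controls the same formula gives 79.4% or 76.9%. A fixed 10% benchmark would give about 96% (exact, 13 or more responses in 75). The stated figure therefore fits a comparison that counts the controls' sampling error and has no covariate.

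**2. Effect of a difference in LAG-3 mix with no dose effect.** Inputs: 18.2% and 5.0% from Section 1.1.6, taken as true; 60% LAG-3-positive controls, the prevalence in Section 8.1.4.1; the Part E share s is varied by assumption.

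ORR(s) = 0.182s + 0.05(1 − s). Controls: 12.92%. One-sided error = P(Z > 1.645 − diff/SE), where SE = √(p₁q₁/75 + p₀q₀/n₀).

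| Part E share | n₀ | Part E ORR | diff | SE | error |
|---|---|---|---|---|---|
| 50% | 150 | 11.60% | −1.32 pts | 4.60 | 2.7% |
| 70% | 150 | 14.24% | +1.32 pts | 4.88 | 8.5% |
| 80% | 150 | 15.56% | +2.64 pts | 5.00 | 13.2% |
| 70% | 61 | 14.24% | +1.32 pts | 5.89 | 7.8% |
| 80% | 61 | 15.56% | +2.64 pts | 6.00 | 11.4% |

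The bias is about 1.3 ORR points for each 10-point difference in share.

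**3. Effect of stratifying on LAG-3.** Simulation of 75 v 150 with the same strata rates and no dose effect, rejecting in the 5% upper tail:

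| Part E share | 40% | 60% | 70% | 80% | 90% |
|---|---|---|---|---|---|
| Crude test | 1.4% | 5.5% | 9.4% | 14.5% | 21.0% |

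The CMH test stratified on LAG-3 stays at 5.2% to 5.4% throughout. The simulated crude test sits slightly above the formula because it already runs at 5.5% when the mix is equal.

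For power, the strata were scaled so that the control ORR is 10% and the 480 mg ORR is 25% at a 60% share. At shares of 40%, 60% and 80%, crude power is 69%, 90% and 98%; CMH power is 86%, 90% and 92%. If about 13% lack a LAG-3 result (8 of 61 in Part C) and are dropped (65 v 130), CMH power is about 87%.

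**4. Precision of the LAG-3 contrast.** 6/33 v 1/20 is a ratio of 3.6 on 7 responders; Fisher's two-sided p = 0.23.

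**5. First-line randomised cohort.** 75 per arm, 67% v 47%: SE = √(0.67×0.33/75 + 0.47×0.53/75) = 0.0792, so power = Φ(0.20/0.0792 − 1.645) = 81.1%, matching the stated 81%. If baseline covariates explain 5% of response variance (an assumption), power = Φ(0.20/(0.0792×√0.95) − 1.645) = 82.8%, a gain of about 2 points.

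**The case against.** The strongest reply is that the shift is hypothetical. Prior-anti-PD-1 eligibility in Part E is almost identical to Part D1, and neither selects on LAG-3. If both groups come from a population with 60% prevalence, the SE of the difference in shares is √(0.24×(1/75 + 1/150)) = 6.9 points, so a 20-point gap would be about 2.9 SE. Chance imbalance of that kind is already covered by the binomial variance. This stands: the inflation requires a systematic difference in mix, and no passage shows one. It is weaker if Part C subjects belong to the control set.

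The LAG-3 effect is also poorly estimated, the 150 controls are not stated in Section 8.1.5, and the strata rates imply a 12.9% control ORR rather than the planned 10%. All of this stands, and it makes the error figures illustrative.

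Section 1.2 says no hypotheses are formally evaluated, and Section 8.1.5 speaks of preliminary efficacy. But Section 1.3.1 aims to demonstrate a significant increase, and the cohort is sized for a test.

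A reader might infer more than the documents support, in four ways:

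- That a crude analysis has been chosen. The Part E method is simply not specified, and Section 8.4.2 refers some detail to an analysis plan that is not in the supplied text.
- That LAG-3 is known to be recorded for every Part E participant. Tissue is mandatory, but Section 3.3.1 tolerates inadequate biopsies and the synopsis lists LAG-3 expression as an exploratory endpoint that may be included.
- That the historical rate is treated as error-free. Step 1 above points the other way.
- That the randomised comparison is biased. It is not; only some precision is at issue, and the LAG-3 rates come from prior-anti-PD-1 patients, so they do not carry over to the first-line cohort.

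**Conclusion.** The point holds for the prior-anti-PD-1 cohort. A comparison serving a primary objective rests on earlier, non-randomised controls, and the plan specifies nothing to handle case mix, while its own data suggest that a measurable baseline marker may matter.

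The size is conditional: a one-sided error of about 8% to 13% in place of 5% if the Part E LAG-3-positive share is systematically 70% to 80% against 60%, and a loss of power if the share is lower. This assumes 150 controls (about 11% rather than 13% at the 80% share with 61) and takes rates based on 7 responders as true. Stratifying on LAG-3 removes this source of error with no material power loss at equal mix, which makes the change worthwhile even if the shift never occurs. The stated power figures are not in error. For the first-line cohort, adjustment is optional.

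**What to change.** In Section 8.4.2, for the prior-anti-PD-1 cohort:

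1. Define the historical control set and its n, and reconcile Section 1.1.7 (160 mg/480 mg Q4W) with Section 8.1.5 (80 mg/240 mg Q2W).
2. State that LAG-3 will be assessed on Part E baseline tissue.
3. Prespecify a LAG-3-stratified (CMH-type) ORR difference with strata of at least 1%, below 1% and unknown, reported alongside the crude difference.
4. Keep standardisation for BRAF, prior ipilimumab and LDH as a sensitivity analysis. At 10% of 150 the controls supply only about 15 responders, too few for a model with several covariates to carry the main estimate.

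For the randomised first-line cohort, a covariate-adjusted ORR difference using baseline values already collected (for example LDH, BRAF and ECOG) may be added for precision.

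The cost is wording and programming, with no added subjects. The downside is that some subjects will have no LAG-3 result; the unknown stratum keeps them in the analysis but does not adjust for their true status.
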